Disease Control Rate (DCR). The confirmed disease control rate is defined as the proportion of subjects in the analysis set who have a confirmed best response of CR, PR, or SD per RECIST v1.1 as assessed by the Investigator. Per RECIST v1.1, CR or PR must be confirmed by a confirmatory assessment performed at least 4 weeks after the initial response. In the case of SD, measurements must have met the SD criteria at least once after study entry at a minimum interval of 6 weeks. Confirmation of SD is not required. OR assessment evaluated after new anti-cancer treatment will not be considered for DCR calculation.

Duration of Response (DOR). Duration of response will be based on RECIST v1.1 as determined by Investigator and calculated for confirmed responders. The DOR will be measured from the time at which criteria are first met for CR or PR

Regeneron Pharmaceuticals Inc. / Protocol: CMP-001-007
IQVIA Biotech (Confidential) Project # SZA56629

(whichever is first recorded) until the first date that recurrence or PD is objectively documented (taking as reference for PD the smallest measurements recorded on study).

DOOR is only defined for subjects who have a confirmed BOR of CR or PR. Subjects with an overall response of CR or PR must have a repeat tumor assessment performed no less than 4 weeks after the criteria for response are first met. The first date at which a CR or PR response was noted will be used to calculate DOOR, not the date of the confirmatory tumor assessment. Subjects who did not have PD or death will be censored at the date of their last disease assessment. For subjects who started a subsequent anti-cancer therapy before having a documented PD, the last disease assessment prior to the start of the subsequent therapy will be used. Censoring rules are detailed in Table 1a.

DOOR will be calculated as follows:

$$\text{DOOR (months)} = (\text{Event/Censoring Date} - \text{Response Start Date} + 1) / 30.4375$$

Progression-Free Survival (PFS). Progression-free survival is defined as the time from first dose of study treatment to the date of documented PD based on RECIST v1.1 by Investigator or death from any cause, whichever occurs first.

PFS will be calculated as follows:

$$\text{PFS (months)} = (\text{Event or Censoring Date} - \text{First Dose Date} + 1) / 30.4375$$

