All events of RECIST v1.1 disease progression or death will be counted regardless of whether the event occurred while the subject was on study drug or had previously discontinued treatment. Subjects who do not experience disease progression or death before the analysis cutoff date will be censored at the date of last adequate tumor assessment. Date of censoring for these subjects will be based on the last tumor assessment prior to missing the assessments. For subjects who started a subsequent anti-cancer therapy before having a documented PD, the overall response assessment evaluated after new anti-cancer treatment will not be considered for PFS calculation, and the last disease assessment prior to the start of the subsequent therapy will be used. Censoring rules are summarized in Table 1a. If a subject meets the criteria for more than one censoring rule, PFS will be censored at the earliest censoring date.

Overall Survival (OS). Overall survival will be calculated as the time from first dose of study treatment to the date of death due to any cause. Subjects who are alive at the time of analyses will be censored at the time of last known alive date, or at data cutoff date, whichever occurs first. Censoring rules are detailed in Table 1c. The last contact date will be derived as [Table 2](#).

Regeneron Pharmaceuticals Inc. / Protocol: CMP-001-007
IQVIA Biotech (Confidential) Project # SZA56629

OS will be calculated as follows:

$$\text{OS (months)} = (\text{Death or Censoring Date} - \text{First Dose Date} + 1) / 30.4375$$

Immune Objective Response Rate (iORR). iORR is defined as the proportion of subjects with a best overall immune response (iBOR) of confirmed immune complete response (iCR) or confirmed immune partial response (iPR) based on immunotherapy Response Evaluation Criteria in Solid Tumors (iRECIST) by Investigator assessment.

Subjects who continue study treatment beyond PD per RECIST v1.1 will be assessed by the Investigator according to iRECIST. Subjects with an iCR or iPR per iRECIST must have a confirmatory assessment performed at least 4 weeks after the initial assessment where response was declared by the Investigator and all scans should be performed at least 2 weeks after the previous CMP-001 IT injection to prevent injection-related pseudo-progression.

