No PD per RECIST v1.1 or Death as of data cutoff date and subject not received new anticancer therapy or received it after the data cutoff date	Censored	Date of last disease assessment on/before data cutoff date	Alive without Documented PD
No PD per RECIST v1.1 or Death as of data cutoff date and new anticancer therapy started before the data cutoff date	Censored	Date of last disease assessment prior to new anticancer therapy	Subsequent Anti-cancer Therapy without Documented PD
PD per RECIST v1.1 or Death after new anticancer therapy and the new anticancer started before data cutoff date	Censored	Date of last disease assessment prior to new anticancer therapy	Documented PD or Death after Subsequent Anti-cancer Therapy
PD per RECIST v1.1 or Death after new anticancer therapy and the new anticancer started after data cutoff date	Censored	Date of last disease assessment on/before data cutoff date	Documented PD or Death after Subsequent Anti-cancer Therapy
PD per RECIST v1.1 or Death immediately following two or more consecutive disease assessments missed since the last adequate disease assessment	Censored	Date of last adequate tumor assessment prior to missing assessments	PD or Death after Missing ≥ 2 Consecutive Disease Assessments
Withdrew consent or lost to follow-up before PD per RECIST v1.1 or Death	Censored	Date of last adequate disease assessment	Discontinued from Study without Documented PD or Death

Table 1b: Censoring Rules for the iPFS/iDOR

Situation	Outcome	Date	Event Description/ Censoring Reason
iCPD per iRECIST between scheduled disease assessments on/before new anticancer therapy or data cutoff date,	Event	Earliest date of tumor assessment documenting iUPD	iCPD per iRECIST

Regeneron Pharmaceuticals Inc. / Protocol: CMP-001-007
 IQVIA Biotech (Confidential) Project # SZA56629

whichever is earlier			
Death without iCPD per iRECIST and not receiving new anticancer therapy on/before data cutoff date	Event	Date of death	Death without iCPD per iRECIST
iPFS only iUPD per iRECIST at the time of PD per RECIST v1.1, continued study treatment without further tumor assessments as of data cutoff date	Censored	Date of the last tumor assessment on/before data cutoff date	No Adequate Disease Assessment per iRECIST

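### The SAP's PFS text gives event-free subjects a pre-missed-scan censoring date that conflicts with Table 1a and, read literally, discards later progression-free follow-up

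*SAP*

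**What the plan says.** The PFS paragraph of SAP Section VIII.A first states that subjects without progression or death before the analysis cutoff "will be censored at the date of last adequate tumor assessment". The next sentence reads: "Date of censoring for these subjects will be based on the last tumor assessment prior to missing the assessments". Grammatically, *these subjects* are the event-free subjects just named. The paragraph then adds "Censoring rules are summarized in Table 1a", followed directly by "If a subject meets the criteria for more than one censoring rule, PFS will be censored at the earliest censoring date".

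Table 1a treats the same subjects differently. Its event-free row ("No PD per RECIST v1.1 or Death as of data cutoff date and subject not received new anticancer therapy", or received after cutoff) sets the date as "Date of last disease assessment on/before data cutoff date", with no condition on missed scans. Its only missed-scan row is for "PD per RECIST v1.1 or Death immediately following two or more consecutive disease assessments missed since the last adequate disease assessment".

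The DOR text in the same section relies on the same table and has no missed-scan clause: "Subjects who did not have PD or death will be censored at the date of their last disease assessment".

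Protocol Section 9.5.4 does not settle the matter. It says that subjects alive and progression-free are censored, gives no date, and leaves further rules to the SAP.

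**The concern.** The SAP gives two censoring dates for one group of subjects and does not say whether the narrative or the table prevails. The narrative sentence sets no threshold for missed scans and makes no exception for a subject who misses a scan, returns and is found progression-free.

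Read literally as any missed scan, the rule depends on outcome. A subject who misses one scan and then progresses stays in as an event under Table 1a. A subject who misses one scan and stays progression-free is cut back to before the gap. Follow-up is then lost only from those doing well, and the later part of the Kaplan-Meier curve falls. SAP Section VIII.C plans event-free rates at landmarks such as 6, 9, 12 and 18 months, and PFS by HPV and PD-L1 subgroup, from 24 treated subjects. A few reassigned dates could be visible in those estimates.

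There is also a smaller wording mismatch. The PFS narrative and two Table 1a rows (missed scans; withdrawal or loss to follow-up) use the last *adequate* assessment. The event-free and new-therapy rows use simply the *last* one. A scan that cannot be evaluated may therefore extend follow-up under one wording and not under the other.

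**Working it through.** The documents give no planning figure for PFS, so there is none to reproduce. The protocol's 43 subjects were sized for ORR and play no part here.

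**Inputs from the documents.** Scans at Week 10 Day 1 and every 9 weeks after that; PFS in months = (event or censoring date − first dose date + 1)/30.4375; 24 treated subjects; Kaplan-Meier estimation; an ad-hoc analysis triggered by two disease assessments after the last enrolment.

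**1. One subject.** Week w Day 1 is study day 7(w − 1) + 1. Take an event-free subject who misses Week 28 and has clean scans at Weeks 37 and 46.
- Table 1a: Week 46, day 316, 316/30.4375 = 10.38 months.
- Narrative read as any missed scan: Week 19, day 127, 127/30.4375 = 4.17 months.
- Difference: 316 − 127 = 189 days, or 6.2 months, and two clean scans.

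**2. A 24-subject illustration (invented counts).** Suppose 10, 5 and 2 events at Weeks 10, 19 and 28.
- Table 1a: (14/24)(9/14)(7/9) = 29.2% after Week 28.
- If 2 of the 7 event-free subjects missed Week 19 and are cut back to Week 10: (14/24)(7/12)(5/7) = 24.3%.
- The median does not move. The curve first falls below 50% at Week 19 either way (37.5% against 34.0%).

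**3. Simulation.** 60,000 subjects per scenario, with every rule applied to the same subjects. Assumptions not in the documents: exponential PFS; scans missed at random; uniform accrual over 18 months; cutoff 19 weeks after last enrolment; deaths not modelled separately. 12-month PFS:

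| Assumed median | Scans missed | No scans missed | Table 1a | Narrative, any missed scan | Narrative, two or more consecutive |
|---|---|---|---|---|---|
| 3 months | 5% | 9.0% | 9.2% | 8.5% | 9.2% |
| 3 months | 10% | 8.9% | 9.3% | 7.8% | 9.1% |
| 3 months | 20% | 9.1% | 10.2% | 7.4% | 9.7% |
| 5 months | 5% | 24.0% | 24.2% | 22.3% | 24.1% |
| 5 months | 10% | 23.8% | 24.6% | 20.9% | 24.2% |
| 5 months | 20% | 23.5% | 25.5% | 18.4% | 24.3% |
| 9 months | 5% | 45.0% | 45.2% | 42.2% | 45.1% |
| 9 months | 10% | 44.7% | 45.5% | 39.3% | 44.9% |
| 9 months | 20% | 45.2% | 47.6% | 35.5% | 45.7% |

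- Any missed scan against Table 1a: lower by 0.7 (9.2 − 8.5) to 12.1 points (47.6 − 35.5). With 12 or 24 months of accrual at a 5-month median, the gap is 1.5 to 10.1 points.
- Two or more consecutive against Table 1a: lower by 0 to 1.9 points across all scenarios run.
- Median under the any-missed-scan reading: unchanged at true medians of 3 and 5 months. At 9 months it drops one scan interval, from 10.38 to 8.31 months, when 10% or 20% of scans are missed.
- Share of subjects whose date is shortened, at a 5-month median with 10% missed and 18-month accrual: 6.1%, or about 24 × 0.061 = 1.5 subjects in this trial.

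**The case against.** The strongest reply is that the sentence is a drafting slip and the intended rule is clear. Its wording nearly repeats the date cell of Table 1a's missed-scan row, so it may be a displaced fragment of that row. It may also mean only subjects who stop being scanned and never return, which gives the same date as the sentence before it. The DOR text supports Table 1a as the intent. Both alternative readings are fair. Neither rescues the sentence: as a fragment it is attached to the wrong subjects, and as a never-return rule it is redundant and does not say so.

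A reader might infer three stronger things that the documents do not support.
- *Any missed scan triggers early censoring.* The text speaks of missed assessments in the plural and sets no threshold. This is one reading, not a stated rule.
- *The tie-breaker makes the narrative override the table.* The tie-breaker directly follows the pointer to Table 1a, so the rules it ranks are most naturally the table's rows. An event-free subject does not meet the missed-scan row, which requires progression or death. The pre-gap date is selected only if the stray sentence counts as a separate rule.
- *PFS is biased downward.* This depends on the reading, the missed-scan rate and the time point. Under the any-missed-scan reading, 12-month PFS is 0.5 to 9.7 points below complete scanning, but the 6-month rate is sometimes slightly above it (by up to 1.4 points), because missed scans delay detection of progression. Under the two-or-more reading, 12-month PFS is within −0.2 to +1.3 points of complete scanning. Table 1a itself runs 0.1 to 2.4 points high at 12 months, since it censors progression after a long gap but keeps event-free subjects with the same gap.

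**Conclusion.** The conflict is real and should be corrected. SAP Section VIII.A states a censoring rule for event-free subjects that disagrees with Table 1a and with the DOR text, and no order of precedence is given. In the literal reading the rule is wrong, because it censors according to later outcome. Its cost is then about 0.7 to 12 points of 12-month PFS relative to Table 1a, under assumed exponential medians of 3 to 9 months and 5% to 20% of scans missed at random. The documents give neither a PFS assumption nor a missed-scan rate, so this is a range and not an estimate for this trial. The median is often unaffected. The effect is small or nil if the sentence means two or more missed scans or subjects who never return.

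PFS is a secondary endpoint and the SAP makes all analyses descriptive and exploratory, so no test or error rate is at stake. What is at stake is whether the PFS dates can be reproduced from the SAP and whether the later landmark rates can be trusted.

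**What to change.** In the PFS paragraph of SAP Section VIII.A:
1. Delete the sentence on missing assessments. State that subjects without PD or death are censored at the last adequate assessment on or before the cutoff and before any new anticancer therapy, whether or not earlier scans were missed.
2. Limit the missed-scan rule to PD or death directly after two or more consecutive missed assessments, as Table 1a already has it.
3. Use either *last* or *last adequate* consistently across the Table 1a rows and the PFS and DOR text. If *adequate* is kept, define it once, including how a not-evaluable scan is treated.
4. State that Table 1a governs where text and table differ.
5. Keep the earliest-date tie-breaker, but say that it applies only among Table 1a rows. It is still needed where rows overlap, for example new therapy together with withdrawal of consent.

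The cost is SAP wording only. No data collection or assessment changes.

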4.5. Treatment Discontinuation

Study treatment should continue until 1 of the following occurs:

- Unacceptable adverse event that precludes further study treatment (see Section 5.1.2.5.4 and Section 5.1.3)
- 2 years of study treatment
- PD per RECIST v1.1; continuation of treatment through suspected pseudo-progression is permitted at the Investigator's discretion until confirmed PD per iRECIST (Section 7.2.5)
- Upon request of the Sponsor or regulatory agency
- Clinical disease progression

- If medically necessary in the opinion of the Investigator
- Subject withdraws consent for treatment (note that a subject who withdraws consent for additional study treatment and procedures but not for antitumor response will continue to be followed)
- Subject becomes pregnant or begins breastfeeding
- Subject is lost to follow-up
- Death
- End of Clinical Trial

Subjects who permanently discontinue treatment with pembrolizumab because of immune-mediated AEs must also permanently discontinue treatment with CMP-001.

Subjects will continue study treatment until they reach a reason for treatment or study discontinuation. Clinically stable subjects may continue study treatment beyond RECIST v1.1 progression based upon Investigator judgement of potential benefit. Study treatment may not continue beyond 2 years from initial dose of study treatment.

If a subject achieves and maintains a confirmed CR or iCR by Investigator review, treatment with CMP-001 or the combination of CMP-001 and pembrolizumab may be discontinued at the Investigator's discretion once they meet both of the following criteria:

- Subject has been treated with both study drugs for at least 24 weeks
- Subject has received at least 3 doses of both study drugs beyond the date of the initial CR/iCR

NOTE: 3 doses are required only if medically feasible in the Investigator's opinion – less than 3 doses are acceptable if the Investigator is not medically able to inject.

Subjects who discontinue study treatment should undergo the EOT assessments per [Table 1](#). Subjects who discontinue study treatment for reasons other than disease progression (per RECIST v1.1 or iRECIST by Investigator, or clinical PD per Investigator) should remain on study for PTFU (Section [7.6](#)) and LTSFU (Section [7.7](#)) and receive disease assessments according to the Schedule of Assessments ([Table 1](#)).

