7.6. Posttreatment Follow-Up

Subjects who discontinue study treatment and transition into PTFU will continue to have assessments collected per the time points specified in the Schedule of Assessments ([Table 1](#)). Post treatment follow-up disease assessments will continue until disease progression, initiation of another cancer treatment, death, lost to follow-up, withdrawal of consent, or End of Clinical Trial.

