The confirmed iORR will be calculated as the number of subjects with a confirmed iCR or iPR divided by the number of subjects in the analysis population [iORR = (confirmed iCR + confirmed iPR)/number of subjects]. The two-sided 95% Clopper-Pearson CIs will be calculated for the iORR.

The best overall immune response (iBOR) will be derived as below:

$$\text{iCR} > \text{iPR} > \text{iSD} > \text{iCPD} > \text{iUPD} > \text{NE}$$

If assessments are not performed or cannot be assessed following iUPD, and there is no subsequent iCPD, iSD, iPR or iCR, iUPD will continue to be used and the subject will be censored at the date of iUPD.

Immune Progression-Free Survival (iPFS). iPFS is defined as the time from date of first dose of study drug to date of iCPD per iRECIST as assessed by Investigator or death, whichever occurs first. Censoring rules are detailed in [Table 1b](#).

Immune Duration of Response (iDOR). iDOR is defined as the time from the date of the first immune response (iCR or iPR) to the date of immune confirmed progressive disease (iCPD) per iRECIST by Investigator assessment.

iDOR is only defined for Subjects who have a confirmed iBOR of iCR or iPR. Subjects with a response of iCR or iPR must have a repeat tumor assessment performed no less than 4 weeks after the criteria for response are first met. The first date at which an iCR or iPR response was noted will be used to calculate iDOR, not the date of the confirmatory tumor assessment. Subjects who did not have iCPD or death will be censored at the date of their last disease assessment. Censoring rules are detailed in [Table 1b](#).

Regeneron Pharmaceuticals Inc. / Protocol: CMP-001-007
 IQVIA Biotech (Confidential) Project # SZA56629

Table 1a: Censoring Rules for the PFS/DOR

Situation	Outcome	Date	Event Description/ Censoring Reason
PD per RECIST v1.1 on/before new anticancer therapy or data cutoff date, whichever is earlier	Event	Earliest date of tumor assessment documenting PD	PD per RECIST v1.1
Death without PD per RECIST v1.1 and not receiving new anticancer therapy on/before data cutoff date	Event	Date of death	Death without PD per RECIST v1.1
[PFS only] Subjects with no post-baseline assessments	Censored	Date of First Dose of Study Drug	No Adequate Disease Assessment per RECIST v1.1

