iUPD per iRECIST, continued study treatment with subsequent disease assessments but no confirmed PD (i.e., iCPD not assigned) or Death as of data cutoff date and subject not received new anticancer therapy or received it after the data cutoff date	Censored	Date of the last tumor assessment as of data cutoff date	Alive without Documented iCPD
iUPD per iRECIST, continued study treatment, but started a new anti-cancer therapy before data cutoff date without evidence of iCPD or Death	Censored	Date of the last tumor assessment prior to new anti-cancer therapy	Subsequent Anti-cancer Therapy without Documented iCPD
iCPD per iRECIST or Death after new anticancer therapy and the new anticancer started before data cutoff date	Censored	Date of last disease assessment prior to new anticancer therapy	iCPD or Death after Subsequent Anti-cancer Therapy
iCPD per iRECIST or Death after new anticancer therapy and the new anticancer started after data cutoff date	Censored	Date of last disease assessment on/before data cutoff date	iCPD or Death after Subsequent Anti-cancer Therapy
iUPD per iRECIST, continued study treatment, iCPD or Death immediately following two or more consecutive disease assessments since the last adequate disease assessment	Censored	Date of last adequate tumor assessment prior to the first missed assessment	iCPD or Death after Missing ≥ 2 Consecutive Disease Assessments
Withdraw consent or lost to follow-up before iCPD per iRECIST or death	Censored	Date of last adequate disease assessment	Discontinued from Study without Documented iCPD or Death

Table 1c: Censoring Rules for the OS

Situation	Outcome	Date	Event Description/ Censoring Reason
Death on/before data cutoff date	Event	Date of death	Death
Alive with study completed before data cutoff date	Censored	Study completion date	Alive on or before study completion date
Alive or death after data cutoff date with study continuing on/till after data cutoff date	Censored	Data cutoff date	Alive on or before data cutoff date

Regeneron Pharmaceuticals Inc. / Protocol: CMP-001-007
 IQVIA Biotech (Confidential) Project # SZA56629

Lost to follow-up prior to data cutoff date	Censored	Last known alive date	Discontinued from study
Discontinued study without death and not lost to follow-up on/prior to data cutoff date	Censored	Date of study discontinuation	Discontinued from study

Table 2: Last Contact Date for the Overall Survival

Source Data	Conditions

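### iPFS censors progression that was never re-imaged, which biases it upward by an amount the documents do not fix (iDOR in the same direction), and two SAP rules conflict over later deaths

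*SAP*

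**What the plan says.** **Endpoints (SAP VIII.A).** "iPFS is defined as the time from date of first dose of study drug to date of iCPD per iRECIST", or death if earlier. iDOR runs from first immune response to confirmed immune progression (iCPD) and exists only for confirmed immune responders. For iDOR, "Subjects who did not have iCPD or death will be censored at the date of their last disease assessment". Both definitions refer to Table 1b for the censoring rules.

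**iUPD that is not followed up (SAP VIII.A).** Directly after the ranking for best immune response: "If assessments are not performed or cannot be assessed following iUPD, and there is no subsequent iCPD, iSD, iPR or iCR", then "iUPD will continue to be used and the subject will be censored at the date of iUPD".

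**SAP Table 1b.** The row "Death without iCPD per iRECIST and not receiving new anticancer therapy on/before data cutoff date" is an event at the date of death. Four rows describe a subject with iUPD. All four are limited to subjects who continued study treatment, and all four censor; one is "iUPD per iRECIST, continued study treatment, but started a new anti-cancer therapy before data cutoff date without evidence of iCPD or Death". Where iCPD is reached, the event is dated back to the iUPD scan.

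**Imaging (Protocol).** Section 4.5 makes RECIST progression a reason to stop, with continuation at the Investigator's discretion. The group it keeps on post-treatment follow-up is "Subjects who discontinue study treatment for reasons other than disease progression". Section 7.6 adds: "Post treatment follow-up disease assessments will continue until disease progression, initiation of another cancer treatment". Other passages go the other way:
- Section 7.2.5 keeps scanning subjects treated beyond progression.
- Appendix E asks for a re-check 4 to 8 weeks after iUPD.
- Table 1 note c gives 3-monthly disease assessments to all who stop treatment without meeting study discontinuation criteria, and Section 4.6 does not list progression among those criteria.

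**The concern.** An iCPD event needs a scan after iUPD. Under Sections 4.5 and 7.6, a subject taken off treatment at first progression has no such scan planned. Table 1 lists an end-of-treatment disease assessment, but within 7 days of stopping (note a), which is normally too soon for the Appendix E re-check. The SAP then removes this subject from the risk set at the moment of progression. Kaplan-Meier assumes that censored subjects go on to have the same risk as those who remain; here they are censored because they progressed.

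Two things are at stake. First, Table 1a counts the same scan as an event for RECIST PFS, so part of any gap between iPFS and PFS would come from this rule and could be read as benefit after pseudoprogression. Second, where the SAP text and Table 1b disagree, two programmers could derive different event indicators from the same data.

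**Working it through.** The plan gives no figure for iPFS or iDOR, so there is none to reproduce. The check traces the rules, then sizes the effect under stated assumptions.

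**1. Outcomes for a subject who stops at iUPD and is not re-scanned**

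| What follows | SAP VIII.A sentence | Table 1b |
|---|---|---|
| Alive, no new therapy | censored at iUPD | no row |
| Death, no new therapy | censored at iUPD | event at death |
| New therapy, no death | censored at iUPD | only row requires continued study treatment |
| New therapy, then death | censored at iUPD | censored at last scan before new therapy |
| Withdrawn or lost | censored at iUPD | censored at last adequate scan |

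No path gives an event at iUPD, and the second line has two contradictory outcomes.

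**2. Closed form.** Assume exponential times. Let *d* be the share of first events that are deaths without progression, and *c* the share of progressors re-imaged and confirmed. Neither is in the documents. If every un-re-imaged iUPD counts as an event, the hazard is λ. If it is censored, the hazard estimated is λ[d + (1 − d)c]. The median is therefore multiplied by 1 / [d + (1 − d)c].

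| c | d = 0.1 | d = 0.3 |
|---|---|---|
| 0.90 | 1/0.910 = 1.10 | 1/0.930 = 1.08 |
| 0.75 | 1/0.775 = 1.29 | 1/0.825 = 1.21 |
| 0.50 | 1/0.550 = 1.82 | 1/0.650 = 1.54 |
| 0.25 | 1/0.325 = 3.08 | 1/0.475 = 2.11 |

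**3. Simulation on the protocol's scan grid.** From the documents: scans at Week 10 Day 1 and every 9 weeks after, that is every 63/30.4375 = 2.07 months. Assumed: exponential times, median time to progression 3 or 6 months, 15% deaths before progression, 6-month median survival after progression, 50% starting new therapy, follow-up 6 to 24 months. Rule A is the SAP VIII.A sentence. Rule B applies the Table 1b death row. Rule C counts un-re-imaged iUPD as an event and gives median iPFS of 4.1 months (3-month case) or 6.2 months (6-month case).

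| c | A, 3-month | B, 3-month | A, 6-month | B, 6-month |
|---|---|---|---|---|
| 0.90 | 4.1 | 4.1 | 6.2 | 6.2 |
| 0.75 | 4.1 | 4.1 | 7.2 | 6.7 |
| 0.50 | 6.2 | 5.5 | 10.3 | 8.4 |
| 0.25 | 8.3 | 6.8 | 14.5 | 10.8 |

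At c = 0.25 the ratio to rule C is 8.3/4.1 = 2.0 to 14.5/6.2 = 2.3 under A, and 6.8/4.1 = 1.7 to 10.8/6.2 = 1.7 under B. Small biases can vanish because medians tend to fall on scan dates.

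**4. Share of progressors censored.** Under A it is 1 − c. Under B, with 25% to 75% starting new therapy, it is 25% to 43% at c = 0.50 and 38% to 64% at c = 0.25.

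**5. At the actual size of 24 subjects.** With c = 0.25, rule A leaves the median not reached in 18% (3-month case) or 39% (6-month case) of simulated trials, against 0% under rule C. iDOR was not simulated.

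**The case against.** The strongest reply is that the VIII.A sentence sits under the best-response derivation, while iPFS is defined to include death and refers to Table 1b. On that reading rule B governs and the bias is smaller. This has force, but it leaves a living subject who stops at iUPD with no applicable row. Nor does it help those who start new therapy, whose later deaths are censored.

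A second reply is that imaging does not simply end at progression: Section 7.2.5, Appendix E and Table 1 note c provide later scans for some or all subjects. That is correct. A reader might infer that the protocol stops imaging at progression; it plans none only for those who stop treatment at progression, and only under Sections 4.5 and 7.6, which conflict with note c.

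Third, the consequences are limited. The SAP calls all analyses descriptive and exploratory, RECIST PFS and DOR are reported alongside, the planned ad-hoc efficacy displays do not name iPFS or iDOR, and censoring reasons will be tabulated. This stands and lowers the severity. The tabulation helps less than it seems, because Table 1b has no censoring reason specific to this case.

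**Conclusion.** The point holds, at moderate severity. As written, the SAP censors informatively at un-re-imaged iUPD and biases iPFS upward. The direction is the same for iDOR, but only among the confirmed immune responders of 24 treated subjects, and its size there is not established. Under the VIII.A sentence the median multiplier is about 1.1 at c = 0.90, 1.5-1.8 at c = 0.50 and 2-3 at c = 0.25, and less under the Table 1b death row. These figures rest on an assumed re-imaging share and exponential times.

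A reader might go further and infer that most true progressors are censored and both endpoints are grossly overstated. The documents do not support that. Under the VIII.A sentence, a majority censored requires c below 0.50, and no rate of treatment beyond progression or of re-imaging is given. The contradiction over deaths after iUPD needs no such assumption. The primary response rate and RECIST v1.1 PFS and DOR are unaffected.

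**What to change.** In SAP VIII.A and Table 1b:
- Count iUPD with no later evaluable assessment as an iPFS/iDOR event, dated at iUPD, when the reason is that the subject stopped study treatment, started new therapy or died. This matches the date Table 1b already uses for confirmed progression.
- Amend the death row: death after such an iUPD follows the rule above, and death without prior iUPD stays an event at death. Bring the new-therapy and withdrawal/lost-to-follow-up rows into line.
- Limit censoring at the iUPD date to subjects still on study treatment whose next scan is not yet due at cutoff.
- Show the current rule as a sensitivity analysis, and report how many subjects had unconfirmed, un-re-imaged iUPD.

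In the protocol, reconcile Table 1 note c with Sections 4.5 and 7.6 on disease assessment after progression.

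The cost is SAP wording and one derivation rule, with no new data. iPFS and iDOR will look less favourable, and some unconfirmed progressions that might have proved to be pseudoprogression will count as events; the sensitivity analysis shows how much that matters.
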